## LIST OF ABBREVIATIONS

ACCORD	Academic and Clinical Central Office for Research & Development - Joint office for The University of Edinburgh and Lothian Health Board
CI	Chief Investigator
CRF	Case Report Form
GCP	Good Clinical Practice
ICH	International Conference on Harmonisation
PI	Principal Investigator
QA	Quality Assurance
REC	Research Ethics Committee
SOP	Standard Operating Procedure
MRI	Magnetic Resonance Imaging
MRS	Magnetic Resonance Spectroscopy
SAE	Serious Adverse Event
LGG	Lower grade glioma
2HG	2-Hydroxyglutarate
IDH	Isocitrate Dehydrogenase
WHO	World Health Organisation
UoE	University of Edinburgh

## 1 INTRODUCTION

### 1.1 BACKGROUND

Isocitrate dehydrogenase I (IDH1) mutation is an important determinant of prognosis in adult glioma, and a key molecular marker in the WHO 2016 guidelines for brain tumours. Presence of the mutation is independently associated with good outcome, and favourable MGMT status (a predictor of therapeutic response). Wild-type IDH genotype is associated with poor prognosis, even in the absence of typical aggressive imaging and histology features. IDH1 is cytosolic, whereas the IDH2 isoform is nuclear. IDH catalyses oxidation of isocitrate to alpha-ketoglutarate, citric acid cycle intermediary metabolites and oncometabolite influencing histone demethylation. IDH mutation produces a heterodimer where the mutant subunit converts alpha-ketoglutarate to 2-hydroxyglutarate (2-HG, a metabolite not present in normal or wild-type tumour cells).

2-HG can be detected non-invasively in vivo, using optimised magnetic resonance proton spectroscopy (MRS) [1]. This is the first tumour imaging biomarker which is specific to an individual genetic mutation. 2D MRS allows 2-HG to be mapped spatially. Methods for quantification of 2-HG levels have been implemented in studies of glioma [2, 3]

Although the presence of 2-HG is associated with good outcome, high or increasing levels of 2-HG appear to be associated with malignant transformation of WHO grade II glioma, and reduction in 2-HG has been demonstrated with treatment response in longitudinal studies [4].

We have previously demonstrated the feasibility of targeting biopsy based on spectroscopic tissue features, by incorporating spheroid virtual targets into neurosurgical navigation systems [5]

2-HG-optimised MRS has been applied elsewhere in glioma research, but has not previously been translated into UK clinical practice. Reliable detection of 2-HG can be technically challenging. Moreover, the exact mechanisms underlying quantitative variation in 2-HG and processes around malignant transformation have not been elucidated, and limited data exist on spatial heterogeneity of 2-HG in relation to IDH mutation within different tumoral regions.

### 1.2 RATIONALE FOR STUDY

The purpose of this work is to bring this advanced imaging technique to Edinburgh:

As a platform to elucidate molecular features associated with malignant transformation that affect 2-HG levels in spatially-defined regions of gliomas.

For clinical translation as part of a multi-modal imaging protocol; pre-surgical risk stratification in low grade glioma for clinical decision-making.

The proposed study is a collaboration between neurosurgery [name], neuroradiology [name], physics [name] and pathology [name], within the context of the Edinburgh Brain Cancer Centre and The University of Glasgow [name].

## 2 STUDY OBJECTIVES

### 2.1 OBJECTIVES

#### 2.1.1 Primary Objectives

The proposed study will:

1. Optimise MRS acquisition and metabolite estimation methodology.
2. Evaluate the feasibility and reliability of 2-HG metabolite quantification in vivo

#### 2.1.2 Secondary Objectives

Evaluation of mutations, gene expression and associated metabolomic features associated with focally elevated 2HG and malignant transformation. To identify other genetic and chemical changes that are associated with aggressive parts of gliomas, by analysing tissue from regions that show high 2HG levels.

## 2.2 ENDPOINTS

### 2.2.1 Primary Endpoint

Assessment of 2-hydroxyglutarate measured spectroscopically in vivo in relation to IDH mutation determined from surgically resected diffuse glioma specimens.

### 2.2.2 Secondary Endpoint

[figure not shown]
Evaluation of mutations, gene expression and associated metabolomic features associated with focally elevated 2HG and malignant transformation.

## 3 STUDY DESIGN

### 3.1 Centres

This prospective single-centre observational imaging biomarker validation study will be conducted at The University of Edinburgh (Department of Clinical Neuroscience, Royal Infirmary of Edinburgh and Edinburgh Imaging RIE facility) and The University of Glasgow (Imaging Centre of Excellence, Queen Elizabeth University Hospital)

### 3.2 Process flow chart

### 3.3 Recruitment

Patients will be recruited through the Edinburgh or University of Glasgow Neurooncology MDT or Low grade glioma clinic by one of the clinical members of the direct care team and informed consent obtained by the research nurse or one of the members of the research team.

### 3.4 Schedule of assessments

Patients who have not received treatment at the time of recruitment to the study will undergo research MRI protocol within 6 weeks prior to surgery.

Patients who have previously undergone biopsy and/or surgical resection and have significant residual disease will be imaged within 6 months of tissue sampling.

### 3.5 Imaging schedule

MRI/MRS data will be acquired at a single timepoint, prior to surgery (or after surgical resection where there is measurable residual disease).

### 3.6 MRI Protocol

MRI examinations will be acquired on 3T Siemens Prisma MRI system in Edinburgh Imaging RIE facility or at the Glasgow ICE facility.

The MRI protocol will be setup by a physicist including the following sequences in addition to standard clinical sequences used in glioma assessment:

Single voxel localised MRS, optimised for detection of 2HG.

### 3.7 Histology

IDH-1, 1p/19q ATRX, P53 and other relevant assays will be carried out on subsequently acquired tissue samples from resection or stereotactic biopsy, as part of standard clinical care; IDH status will be compared with in vivo MRS detected 2-HG. Histological analyses will be performed by [name] (NHS and University of Edinburgh) using standard clinical pathways. Additional proteomic, metabolomic and gene expression tissue analysis will also be performed.

### 3.8 Follow-up

Patients will have their clinical data recorded for the purpose of the study.

### 3.9 Data Storage and Transfer

Imaging and histology data will be anonymised and transferred to University of Edinburgh BRICIA server encrypted so it will only be accessible by specific members of the research team. All data will be linked anonymised prior to being analysed.

## 4 Study Population

### 4.1 NUMBER OF PARTICIPANTS

20 lower grade glioma patients (LGG) will be selected to participate in this study, recruited through the Edinburgh Neurooncology MDT or University of Glasgow Low grade glioma clinic by one of the clinical members of the direct care team.

**Commented [TS1]:** What is the role of the Glasgow centre?

**Commented [ML2R1]:** Glasgow partners will identify patients for recruitment.

**Commented [TS3R1]:** Will the participants then come to Edinburgh? If Glasgow is only recruiting, they could be added as a PIC (participant identification centres) – more info [here](#). It could simplify the application and contracts process, please add more details here and select in PART C of IRAS for the Glasgow site that it is a PIC.

**Commented [TS4]:** Please detail which platform/servers are these

**Commented [TS5]:** Is this in Queen Elizabeth or RIE?

## 4.2 INCLUSION CRITERIA

- Adult subjects; 18-75 years old.
- Radiologically suspected diffuse lower grade glioma (LGG):
  1. In whom resection is planned, or
  2. Histologically-proven IDH mutant diffuse glioma and significant post-surgical tumour residuum.
  3. Must be able to provide informed consent.

Commented [TS6]: This needs to match A17-1 from IRAS

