## 6.3 STORAGE AND ANALYSIS OF SAMPLES

Biopsy samples will be collected and stored within the NHS pathology lab as consistent with the standard of care.

Histologic analyses will be performed in [name] laboratory using standard clinical pathways. Additional proteomic, metabolomic and gene expression tissue analysis will also be performed. Samples will be kept as with standard of care, and histological data and analysis will be anonymised and transferred to University of Edinburgh BRICIA server. All data will be linked anonymised prior to being analysed.

The data from these biological samples will be used to correlate with the non-invasive imaging analysis to determine whether the molecular markers as determined with imaging matches with the tissue molecular markers.

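### One of two entry routes admits only proven IDH mutants and no split is set, so the primary 2HG-versus-IDH comparison may have few or no wild-types and, if left undivided, mixes IDH status with surgical status

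*Protocol*

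**What the plan says.** Protocol 3.1 describes an "imaging biomarker validation study". The primary endpoint in 2.2.1 is "Assessment of 2-hydroxyglutarate measured spectroscopically in vivo in relation to IDH mutation determined from surgically resected diffuse glioma specimens". Section 3.7 adds that "IDH status will be compared with in vivo MRS detected 2-HG", and 6.3 gives the purpose: "to determine whether the molecular markers as determined with imaging matches with the tissue molecular markers". Section 9.2 sets tissue results against MRS data without distinguishing groups of participants.

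On numbers, 4.1 states that "20 lower grade glioma patients (LGG) will be selected to participate in this study". Section 4.2 gives two alternative routes for a suspected lower grade glioma. The first ("In whom resection is planned, or") leaves IDH status open. The second is "Histologically-proven IDH mutant diffuse glioma and significant post-surgical tumour residuum". No section gives a number or share for either route, a limit on the second, or a minimum number of wild-types. Section 9.1 gives no group ratio.

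On tissue, 2.2.1 speaks of resected specimens and 4.2 item 1 of planned resection. Section 3.7 uses "subsequently acquired tissue samples from resection or stereotactic biopsy", 4.3 accepts patients who can have either procedure, and 6.1 also provides for biopsy.

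**The concern.** Section 1.1 says that wild-type cells do not contain 2HG. Wild-type tumours are therefore where false positives would show, and without them the endpoint has nothing to compare the mutants with. The second route selects on the reference standard: its IDH result is mutant by definition and known before the scan.

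Two consequences follow. First, the number of wild-types is left to chance and to the enrolment mix, and full compliance with the protocol allows it to be zero.

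Second, every wild-type would be an unoperated tumour, while the mutants may include residual tumour scanned up to six months after surgery. A difference in 2HG between mutants and wild-types could then partly reflect surgical status. Overall accuracy and predictive values would depend on how many known mutants were enrolled, whereas 1.2 names risk assessment before surgery as the clinical use.

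**Working it through.** **The plan's own figure.** The sample size of 20 cannot be reproduced. Section 9.1 cites earlier work but gives no significance level, power, effect size, SD, expected rates or group ratio.

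**Inputs.** N = 20 (4.1). R = number entering by the second route, and w = wild-type share in the first route. The protocol gives neither R nor w, so both are assumed and shown as ranges.

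**Number of wild-types.** The count is Binomial(20 − R, w), so its mean is (20 − R)w and P(none) = (1 − w)^(20 − R).

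| R | Expected at w = 0.1 / 0.2 / 0.3 | P(none) |
|---|---|---|
| 0 | 2 / 4 / 6 | 0.12 / 0.01 / 0.001 |
| 10 | 1 / 2 / 3 | 0.35 / 0.11 / 0.03 |
| 15 | 0.5 / 1 / 1.5 | 0.59 / 0.33 / 0.17 |
| 20 | 0 / 0 / 0 | 1 / 1 / 1 |

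With w = 0.5, the expected number is 10 at R = 0 and 5 at R = 10.

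**Precision of specificity.** If all k wild-types test negative, the exact (Clopper-Pearson) 95% lower limit is 0.025^(1/k). This gives 0.16 for 2/2, 0.29 for 3/3 and 0.40 for 4/4.

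**Predictive values.** Assume sensitivity 0.90, specificity 0.70, R = 10 and w = 0.2.
- Pre-surgical only (2 wild-types, 8 mutants): NPV = 2 × 0.70 / (2 × 0.70 + 8 × 0.10) = 1.4/2.2 = 0.64.
- With the 10 known mutants added (2 wild-types, 18 mutants): NPV = 1.4 / (1.4 + 18 × 0.10) = 1.4/3.2 = 0.44.

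The test is the same in both lines; only the mix has changed.

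**Overall accuracy.** A test that calls everyone mutant scores 1 − (20 − R)w/20. At w = 0.3 this is 0.70, 0.85 and 1.00 for R = 0, 10 and 20.

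**Confounding with surgical status.** With R = 10 and w = 0.2, 10 of the 18 mutants (0.56) are post-surgical. If their mean 2HG differs from that of pre-surgical mutants by δ, the undivided mutant-versus-wild-type difference shifts by 0.56δ. The protocol gives no value or direction for δ.

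**What separation does not change.** The second route adds no wild-types. Numerator and denominator of specificity are the same with or without it, and so is P(none).

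**The case against.** The strongest reply is that the primary objectives in 2.1.1 are optimisation, feasibility and reliability of 2HG quantification. Patients known to carry the mutation suit those aims, because their tumours should contain the metabolite. That stands: the second route is a defensible choice for 2.1.1. The weakness concerns the endpoint in 2.2.1 and the validation aim in 3.1.

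It can also be said that the protocol names no accuracy measure and that a separate analysis plan, not available here, may divide the cohorts. The first part is true, and a reader who infers that a pooled accuracy figure is planned goes beyond the text. But eligibility and the primary endpoint are protocol content, and the comparison is described there without any division.

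Four further readings are tempting and not supported:
- That half of the participants will be known mutants. There are two routes, but no share is stated.
- That the study will lack wild-types. The first route can supply them: if all 20 entered by it with 20 to 50% wild-type, 4 to 10 would be expected.
- That known mutants distort specificity. They do not enter it; the difficulty is how few wild-types may remain to estimate it.
- That biopsied participants, or those whose lesion is not a diffuse glioma, will be dropped after scanning. No section excludes them from analysis, and 3.7 assays biopsy tissue. What the documents show is inconsistent wording.

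**Conclusion.** The point holds in this form: one route admits only IDH mutants, no split is set, and the primary comparison in 20 patients may therefore have few or no wild-types. Because all wild-types would be pre-surgical, an undivided comparison mixes IDH status with surgical status, and any overall accuracy or predictive value describes the enrolment mix rather than the population in 1.2.

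The size depends on two quantities that the protocol does not give. Under an even split with 10 to 30% wild-type among pre-surgical participants, one to three wild-types are expected, with a 35% to 3% chance of none. Even flawless specificity on such numbers would be compatible with a poor test. More pre-surgical enrolment or a higher wild-type share would ease this; more post-surgical enrolment would worsen it. The 0.64 to 0.44 change in NPV also rests on an assumed sensitivity and specificity, and only illustrates dependence on the mix.

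**What to change.** In 2.2.1 and 9.2:

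1. Base the mutant-versus-wild-type 2HG comparison, and any specificity, AUC or predictive value, on the pre-surgical cohort.
2. Report the post-surgical cohort separately, for detection rate and feasibility only.
3. Report the number of wild-types with exact intervals. If there are none or very few, state that specificity cannot be assessed and limit the conclusion to feasibility and detection.
4. Reconcile the specimen wording in 2.2.1 and the planned resection in 4.2 item 1 with the biopsy wording in 3.7, 4.3 and 6.1. Every scanned pre-surgical participant with resected or biopsied tissue should count in the primary comparison, whatever the final histology.

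The change needs no extra patients or procedures. Its cost is precision. Take 2 wild-types with 8 rather than 18 mutants, and a common SD. The standard error factor rises from √(1/2 + 1/18) = 0.745 to √(1/2 + 1/8) = 0.791, and the t multiplier from 2.101 (18 df) to 2.306 (8 df). The interval is wider by (0.791 × 2.306)/(0.745 × 2.101) = 1.17, about one sixth. The lower limit for perfect sensitivity falls from 0.025^(1/18) = 0.81 to 0.025^(1/8) = 0.63.

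These steps make the result interpretable but do not create wild-types. Only the enrolment mix can do that.

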## 4.3 EXCLUSION CRITERIA

- Any absolute contraindication to MRI.
- Patients unable to tolerate MRI, for example due to claustrophobia or inability to lie flat.
- Patients who are unable to undergo surgical tumour resection or biopsy.
- ECOG Performance status >1 (restricted in strenuous activity but ambulatory and able to carry out light work).
- Patients whose tumours are too small or in anatomical brain locations that make acquisition of satisfactory quality imaging/spectroscopy data impractical.
- Patients who are unable to give informed consent to participation.

Commented [TS7]: This needs to match A17-2 from IRAS

# 5 PARTICIPANT SELECTION AND ENROLMENT

## 5.1 IDENTIFYING PARTICIPANTS

Patients will be recruited through the Edinburgh Neurooncology MDT or Low grade glioma clinic by one of the clinical members of the direct care team and informed consent obtained by the research nurse or one of the members of the research team.

## 5.2 CONSENTING PARTICIPANTS

Participants will have atleast 24 hours to consider the participant information sheet before being involved in the study.

### 5.2.1 Withdrawal of Study Participants

Participants are free to withdraw from the study at any point or a participant can be withdrawn by the Investigator. If withdrawal occurs, the primary reason for withdrawal will be documented in the participant's case report form if possible. The participant will have the option of withdrawal from:

(i) all aspects of the study but continued use of data collected up to that point. To safeguard rights, the minimum personally-identifiable information possible will be collected.

# 6 STUDY ASSESSMENTS

## 6.1 STUDY ASSESSMENTS

Patients will be recruited for the study by members of the direct clinical care team, [either at the Edinburgh site or Glasgow site](#). Pre-surgical patients, after being assessed for eligibility criteria and

providing consent, will undergo research MRI protocol within 6 weeks prior to surgery [\(at their respective site\)](#). During standard of care surgery/biopsy, a portion of the removed tissue will be used to assess molecular biomarkers for clinically relevant metabolic changes in patient's tumour.

Participants who are enrolled post-surgery with significant residual disease will undergo research MRI protocol within 6 months of their surgical resection of tissue.

Assessment	Screening	6 weeks prior to surgery	Day of surgery/biopsy	Post-surgical period (up to 6 months)
Assessment of Eligibility Criteria				
Written informed consent				
Demographic data, contact details				
MRI/MRS scan (pre-surgical participants ONLY)				
Biopsy sample collected				
MRI/MRS scan (post-surgical participants ONLY)				
Molecular analysis of biopsy sample				

## 6.2 LONG TERM FOLLOW UP ASSESSMENTS

There is no plan for long term follow-up.

## 6.3 STORAGE AND ANALYSIS OF SAMPLES

Biopsy samples will be collected and stored within the NHS pathology lab as consistent with the standard of care.

Histologic analyses will be performed in [name] laboratory using standard clinical pathways. Additional proteomic, metabolomic and gene expression tissue analysis will also be performed. Samples will be kept as with standard of care, and histological data and analysis will be anonymised and transferred to University of Edinburgh BRICIA server. All data will be linked anonymised prior to being analysed.

The data from these biological samples will be used to correlate with the non-invasive imaging analysis to determine whether the molecular markers as determined with imaging matches with the tissue molecular markers.

## 7 DATA COLLECTION

Research team members will collect consent forms, patient clinical information, imaging data (MRI and MRS) and perform analysis. Data from pathological analysis will be pseudo anonymised with linking codes. The linked codes will be kept within NHS and the pseudo anonymized data will be kept with the University of Edinburgh BRICIA server. This data will all be kept within the study team and only seen by the appropriate members of the study team.

All University of Edinburgh employed researchers and study staff will complete the Data Protection Training through Learn. All University of Edinburgh employed researchers, students and study staff will complete the Information Security Essentials modules through Learn and will have read the minimum and required reading setting out ground rules to be complied with.

Commented [TS8]: Which one of them? The link will be in the NHSL and the pseudo-anonymise data in UoE?

### 7.1 Source Data Documentation

Source data is defined as all information in original records and certified copies of original records or clinical findings, observations, or other activities in a clinical study necessary for the reconstruction and evaluation of the study. Source data are contained in source documents.

Source documents are original documents, data and records where source data are recorded for the first time.

## 8 DATA MANAGEMENT

[figure not shown]
### 8.1 Personal Data

Precautions will be taken to ensure that patient confidentiality is preserved at all times. The PIS will identify those individuals who will require access to patient data and identifiable details and obtain appropriate permission from the consenting patient. The following personal data will be collected as part of the research: CHI number which will be used to link clinical data to anonymised imaging and tissue data, medical records related to glioma treatment.

Commented [TS9]: Any other data collected apart from CHI? If so, please amend the PIS.

### 8.2 Data Information Flow

Imaging data will be stripped of patient identifiers using well-tested methods, prior to storage and analysis on University BRICIA server. Anonymized imaging/histology data from the University of Glasgow will also be stored on the BRICIA server. Imaging and tissue data will be pseudoanonymised with linking codes, which will stored securely on separate password protected media stored within the CI's pass-protected office in locked cabinets. Data will only be shared within the study team.

### 8.3 Data Storage

Anonymised digital data will be stored in a secure drive on the University of Edinburgh BRICIA, which is password protected and access restricted to only the specific members of the research group given permission by the University IT team.

Personal data will be physically stored by the research team at secure locked file cabinets only accessible by the CI in their pass-protected office at the Royal Infirmary of Edinburgh.

Commented [TS10]: Are the cabinets locked? Detail location.

#### 8.4 Data Retention

Personal data and data generated by the study will be stored for 3 years.

Documents should be stored in such a way that they can be accessed/data retrieved at a later date. The data for this study will be maintained on a secure, password protected East Lothian NHS Trust computer, with only authorised personnel having access to them.

No study document will be destroyed without prior written agreement between the Sponsor and the PI. Should the PI wish to assign the study records to another party or move them to another location, written agreement must be obtained from the Sponsor.

The results of the study will be written and will be submitted for publication to a suitable journal.

